#### 7.1.10.2. Physical Examination

Complete physical examination will be conducted at the scheduled visits prior to dosing shown in the Schedule of Assessments [Appendix 2].

#### 7.1.10.3. Neurological Examination

Neurological examination will be conducted at the scheduled visits prior to dosing shown in the Schedule of Assessments [Appendix 2]. The neurological examination should include level of consciousness, speech, cranial nerves [including pupil equality and reactivity], motor assessment, sensory assessment, coordination, gait, reflexes, and Romberg test.

#### 7.1.10.4. Height and Weight Measurements

Height will be collected at the Screening – Part 2 Visit only. Weight measurement will be taken at the Screening – Part 2 Visit and at all post treatment clinic visits as shown in the Schedule of Assessments [Appendix 2].

Confidential Page 58 of 115

## 7.1.10.5. Vital Signs

Vital sign measurements (blood pressure [BP], pulse, respiratory rate, and body temperature) will occur prior to dosing, lumbar puncture (LP), and blood draw, where applicable. BP and pulse will be measured after the subject is sitting for at least 5 minutes. All BP measurements should be performed in the same arm while sitting, preferably by the same person with an inflatable cuff and a calibrated manometer. Vital signs will be taken at the scheduled visits shown in the Schedule of Assessments [Appendix 2].

After the last blood collection in a visit, subjects will be observed for approximately 15 minutes. BP and pulse will be measured and documented at the end of this observation period.

# 7.1.10.6. Brain Imaging

Brain MRI scans will be scheduled and performed within the window specified for each visit shown in the Schedule of Assessments [Appendix 2].

The screening MRI report per central reader will be used to determine study eligibility, by excluding other neuropathologies, and as baseline for volumetric assessment of the imaging biomarkers. Post dose MRI will be used for safety monitoring and for volumetric MRI assessment of the imaging biomarkers.

MRIs will be performed using either 1.5 or 3 Tesla scanners. Details of the MRI sequences are described in the MRI study manual.

Sedation is permitted for claustrophobic subjects who have difficulty tolerating the MRI procedure according to local standard procedures. For those who cannot undergo MRI, CT is acceptable at Screening but requires prior approval by Medical Monitor. These subjects will not be scheduled for further CT imaging and will not contribute to the assessment of the volumetric imaging biomarkers. CT is not allowed for subjects at sites in Germany.

#### 7.1.10.7. Electrocardiogram

ECGs will be performed as shown in the Schedule of Assessments [Appendix 2]. A standard triplicate 12-lead ECG will be performed at the Screening – Part 2 Visit, Week 6, and Week 13. At subsequent visits, a single 12-lead ECG will be performed unless there is evidence of QT prolongation previously or in or current visit, in which case a triplicate ECG must be performed. The ECG should be obtained after the subject has rested in a supine position for at least 5 minutes. This assessment may be performed any time before blood sampling or at least 30 min after blood sampling, if applicable.

ECG intervals (e.g., interval representing the time for both ventricular depolarization and repolarization to occur [QT interval], QTcF interval, interval from the beginning of the Q wave to the termination of the S wave, representing the time for ventricular depolarization [QRS duration], and time from the onset of the P wave to the start of the QRS complex [PR interval]) and any clinically significant findings will be recorded. The tracings will be reviewed and reported by the central ECG reader.

#### 7.1.10.8. Columbia-Suicide Severity Rating Scale

The C-SSRS will be performed prior to dosing to assess suicide risk at the visits shown in the Schedule of Assessments [Appendix 2].

Confidential Page 59 of 115

# 7.1.10.9. Safety Laboratory Assessments

Safety laboratory tests are summarized in [Table 2]. Clinical chemistry, hematology, coagulation tests, and urinalysis will be performed in all subjects at the scheduled visits shown in the Schedule of Assessments [Appendix 2]. At each visit, blood tests will be done after the completion of all study procedures except for study drug dosing and dispensing.

Confidential Page 60 of 115

**Table 2** Clinical Laboratory Tests

Panel/Assessments	Visits	Parameters to be Analyzed
Genotyping (Blood)	Screening – Part 1 only	APOE genotype
Immunology	Screening – Part 2 only	HIV-1/-2 Ag and Ab
		Hep B S Ag
		Hep C Ab
		HCV RNA (if applicable)
Clinical Chemistry	Screening – Part 2 only	HbA1c
		Vitamin B12
		TSH
		FSH (all females of non-childbearing potential only)
		hCG (all females of childbearing potential only)
Clinical Chemistry	Screening – Part 2,	Albumin
	Weeks 6, 13, 26, 39, 52, 65,	ALP
	78, and ET	AST
		ALT
		GGT
		TBL
		Direct bilirubin
		Indirect bilirubin
		Lactate dehydrogenase
		Blood urea nitrogen
		Creatinine*
		Glucose
		Magnesium
		Potassium
		Sodium
		Total protein
		Calcium
		Chloride
		Phosphorus
TT 4.1	G : D + 2	Uric acid
Hematology	Screening – Part 2,	Hemoglobin
	Weeks 6, 13, 26, 39, 52, 65,	Hematocrit RBC count
	78, and ET	
		RBC MCV White blood cell count with differential (percentage of neutrophils,
		lymphocytes, monocytes, eosinophils, basophils) Platelet count
Coagulation Tests	Screening – Part 2,	aPTT
Coagulation Tests	Weeks 6, 13, 26, 39, 52, 65,	PT
	78, and ET	INR for PT
Urinalysis	Screening – Part 2,	Color
Officialysis	Weeks 6, 13, 26, 52, 78,	
	and ET	Appearance pH
	and L1	Specific gravity
		Glucose
		Protein
		Ketones
		Blood
		Microscopic examination (RBC, white blood cells, epithelial cells,
		casts, crystals, bacteria)
		Urine pregnancy test (all females of child bearing potential only) at
		all visits except Screening – Part 2

ALT: alanine aminotransferase; ALP: alkaline phosphatase; aPTT: activated partial thromboplastin time; AST: aspartate aminotransferase; ET: early termination; FSH: follicle-stimulating hormone; GGT:  $\gamma$ -glutamyl transferase; HbA1c: glycosylated hemoglobin; hCG: human chorionic gonadotropin; HCV RNA: hepatitis C virus RNA; Hep B S Ag: hepatitis B surface antigen; Hep C Ab: hepatitis C antibody; HIV: human immunodeficiency virus; INR: International normalized ratio; MCV: mean corpuscular volume; PT: prothrombin time; RBC: red blood cells; TBL: total bilirubin; TSH: thyroid-stimulating hormone

Confidential Page 61 of 115

\* Used to calculate glomerular filtration rate according to the Modification of Diet in Renal Disease formula.

It is preferred that urine samples for urinalysis and other urine testing is collected at the first void performed at the clinic. All clinical laboratory samples and urine samples for urinalysis will be analyzed at a central laboratory. The urine pregnancy test, if applicable, will be analyzed at the study site.

All laboratory reports must be reviewed, initialed, and dated by the Principal Investigator or by a Sub-Investigator who is a physician or other qualified health care professional involved in the study conduct at the site. Each abnormal test will be evaluated as clinically significant or not clinically significant. All clinically significant abnormal laboratory values that represent an unexpected CBL should be assessed as AEs, and an AE eCRF must be completed. Any clinically significant abnormal values that persist should be followed until they have been resolved or the Investigator, in consultation with the Medical Monitor, assesses them to be chronic or stable.

#### 7.1.10.10. Serum FSH or hCG Test

Serum FSH levels will be measured only for female subjects of non-childbearing potential at the Screening – Part 2 Visit. Serum human chorionic gonadotropin (hCG) levels will be measured only for female subjects of childbearing potential at the Screening – Part 2 Visit.

Serum FSH levels for female subjects of non-childbearing potential should be in the postmenopausal range as determined by the laboratory for study entry. Serum hCG levels for female subjects of childbearing potential must indicate negative pregnancy results for study entry.

## 7.1.10.11. Urine Pregnancy Test

Urine pregnancy test will be performed at subsequent visits prior to dosing shown in the Schedule of Assessments [Appendix 2] for females of childbearing potential. Pregnancy tests must be negative to continue the study.

## 7.1.10.12. Urine Drug Screen

Urine drug screen will be performed at the Screening – Part 2 Visit as shown in the Schedule of Assessments [Appendix 2]. Drugs of abuse to be screened for include amphetamines, MDMA, barbiturates, benzodiazepines, cannabinoids, cocaine, phencyclidine, ethanol, and opiates.

Subjects who use cannabidiol (CBD) oil must commit to withholding consumption for at least 24 hours prior to all clinic visits.

# 7.1.10.13. Screens for HIV and Hepatitis B and C

HIV antigen and antibody, hepatitis B surface antigen (Hep B S Ag), and hepatitis C antibody (Hep C Ab) and HCV RNA (if applicable) tests will be conducted at the Screening – Part 2 Visit as shown in the Schedule of Assessments [Appendix 2].

#### 7.1.11. Clinical Efficacy Assessments

All clinical efficacy assessments will be collected on electronic tablets and will be considered source data. In the uncommon event that a tablet is not functional, assessments will be collected on paper and considered as the source data, and will be entered into the tablet later.

Confidential Page 62 of 115

#### 7.1.11.1. Alzheimer's Disease Assessment Scale – Cognitive Subscale

The ADAS-Cog is a brief neuropsychological assessment used to assess the severity of cognitive symptoms. The ADAS-Cog 13 consist of 13 questions including word recall task, naming objects and fingers, following commands, constructional praxis, ideational praxis, orientation, word recognition task, remembering test directions, spoken language, comprehension, word-finding difficulty, delayed word recall, and digit cancellation tasks. The total test score ranges from 0 to 85. The worse the cognition (cumulative number of errors), the greater the score.

The ADAS-Cog 11 includes all of above items except for delayed word recall and digit cancellation tasks with a total score ranging from 0 to 70.

The ADAS-Cog will be administered, while audio-recorded, to the subject by properly certified site staff at the visits shown in the Schedule of Assessments [Appendix 2]. It is highly recommended that the same rater for a given subject perform the ADAS-Cog throughout the study.

#### 7.1.11.2. Amsterdam Instrumental Activities of Daily Living

The A-IADL Questionnaire is a 70-item informant-based computerized questionnaire aimed at detecting deficits in complex functions at the early stages of AD [Sikkes et al. 2013]. It will be assessed at the visits shown in the Schedule of Assessments [Appendix 2]. Instrumental ADL can be described as the activities necessary to function independently in society. These activities include, but are not limited to, cooking, doing finances, and shopping. They are complex everyday tasks, determined by multiple cognitive processes and controlled processing. They can be distinguished from basic ADL, which include basic self-care skills.

## 7.1.11.3. Disability Assessment for Dementia

The DAD evaluates the basic and instrumental activities in daily activities of subjects with dementia. The proxy-respondent scale specifically measures daily living tasks in terms of executive functions.

A 40-item scale is part of the DAD, which addresses a range of functional domains: eating, meal preparation, telephoning, hygienic, dressing, medication, corresponding, finance, leisure, and housework.

The DAD will be administered to the subject by properly qualified and trained site staff at the visits shown in the Schedule of Assessments [Appendix 2].

#### 7.1.11.4. Clinical Dementia Rating – Global Score and Sum of Boxes

The CDR is a global rating scale used to assess the stage and severity of dementia. It uses a structured, clinician-rated interview that collects information on cognitive and functional capacity from both the subject and caregiver, on performance in six areas (memory, orientation, judgment and problem solving, community affairs, home and hobbies, and personal care). Each of the six areas (boxes) is rated on a scale of 0, 0.5, 1, 2, or 3 where 0 is normal, 0.5 is *Questionable* and 3 is *Severe*. The scores of each of the areas are added together to determine the Sum of Boxes (SB) score. The CDR-SB is used as measurement of efficacy response. A Global Score will also be calculated.

Confidential Page 63 of 115

The CDR will be administered by qualified and trained raters at the site during the Screening – Part 2 Visit to determine eligibility for entry into the study based on the global score, and at the visits shown in the Schedule of Assessments [Appendix 2].

It is important to ensure that a CDR rater is not influenced by knowledge of the ADAS-cog and/or MMSE scores. Therefore, for a given subject, the interview-based CDR should be administered by one rater, while the ADAS-Cog and/or MMSE should be administered by a different rater at the Screening – Part 2 Visit and beyond.

- A CDR rater should not access the ADAS-cog and/or MMSE scores before administering the CDR interview.
- For each subject, it is highly recommended that the CDR rater remains the same throughout the study period.
- A CDR rater may administer clinical scales except for ADAS-cog and MMSE.
- A CDR rater may have access to other clinical data except for ADAS-cog and MMSE.
- A rater may be assigned to administer the CDR for one subject and be assigned to perform the ADAS-cog and/or MMSE for another subject.

# 7.1.11.5. Repeatable Battery for the Assessment of Neuropsychological Status (RBANS) – Delayed Memory Index Score

The RBANS identifies and characterizes abnormal cognitive decline in older adults and serves as a screening battery for younger subjects [Randolph et al. 1998]. The entire battery yields scaled scores for five cognitive domains: Immediate Memory, Visuospatial/Constructional, Language, Attention, and Delayed Memory. The Delayed Memory domain includes List Recall, List Recognition, Story Memory, and Figure Recall.

The Delayed Memory test will be administered by qualified and trained raters at the site during the Screening – Part 2 Visit [Appendix 2]. The Delayed Memory Index Score will serve to determine eligibility for study enrollment.

#### 7.1.11.6. Mini-Mental State Examination

The MMSE is a brief cognitive test assessing general cognitive function that has been used in numerous clinical studies of FDA products approved for the treatment of AD. It will be administered by qualified and trained raters at the site at the visits shown in the Schedule of Assessments [Appendix 2]. MMSE at the Screening – Part 1 Visit can be performed by any qualified rater, while at the Baseline Visit and beyond, the same rater for a given subject is preferred throughout.

The MMSE score from the Screening – Part 1 Visit serves to assess subject eligibility for the study. The MMSE score from the Baseline Visit is used to stratify eligible subjects in the study. The MMSE will also be used as an exploratory measure of efficacy.

#### 7.1.11.7. Neuropsychiatric Inventory

The NPI 12-item form is designed to be a self-administered questionnaire completed by caregivers about subjects for whom they care. Each of the 12 NPI domains contains a survey question that

Confidential Page 64 of 115

reflects cardinal symptoms of that domain. Initial responses to each domain question are "Yes" (present) or "No" (absent). If the response to the domain question is "No", the informant goes to the next question. If "Yes", the informant then rates both the Severity of the symptoms present within the last month on a 3-point scale and the associated impact of the symptom manifestations on them (i.e., Caregiver Distress) using a 5-point scale. The NPI provides symptom Severity and Distress ratings for each symptom reported, and total Severity and Distress scores reflecting the sum of individual domain scores.

The NPI will be administered to the subject by properly qualified and trained site staff at the visits shown in the Schedule of Assessments [Appendix 2].

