NPI-12: Early AD patients may experience various neuropsychiatric symptoms that emerge and worsen with disease progression and contribute to the morbidity and healthcare burden of AD (Forester 2019). The NPI assesses the neuropsychiatric or behavioral symptoms of AD, including their frequency and severity (Cummings 1997). It is a self-administered questionnaire completed by caregivers about subjects for whom they care. The NPI-12 has 12 sub-items, each item has score range of 0-12 with a NPI-total score range of 0-144 for subject's symptoms and 0-60 for caregiver distress (Table 14). Higher scores on each NPI sub-item indicate more severe or frequent occurrence of that symptom. Higher scores on NPI-12 indicate more severe burden of neuropsychiatric or behavioral symptoms.

The same imputation algorithm will be applied to the NPI-12 and Caregiver Distress. If 2 or fewer of 12 items (<25%) of the NPI-12 are missing, the total score will be imputed by prorating the sum from the other completed items: Total score = total score from the completed items × [maximum total score (=144) / maximum total score corresponding to the completed items]. If 2 or fewer of 12 items (<25%) of the Caregiver Distress are missing, the total Caregiver Distress score will be and derived and imputed by prorating the sum from the other completed items: Total Caregiver Distress score = total score from the completed items × [maximum total score (=60) / maximum total score corresponding to the completed items].

The imputed number will be rounded up to the nearest integer. If the scores from more than 2 items are not available, the NPI-12 at that visit will be considered missing.

Table 14 NPI-12 Items and Algorithm for derivation of Item Scores and Total Score

Item	Algorithm	Range	Caregiver Distress Range
Delusions	Frequency (0-4), Severity (0-3)	0-12	0-5
Hallucinations	Frequency (0-4), Severity (0-3)	0-12	0-5
Agitation/Aggression	Frequency (0-4), Severity (0-3)	0-12	0-5
Depression/Dysphoria	Frequency (0-4), Severity (0-3)	0-12	0-5
Anxiety	Frequency (0-4), Severity (0-3)	0-12	0-5
Elation/Euphoria	Frequency (0-4), Severity (0-3)	0-12	0-5
Apathy/Indifference	Frequency (0-4), Severity (0-3)	0-12	0-5
Disinhibition	Frequency (0-4), Severity (0-3)	0-12	0-5
Irritability/Lability	Frequency (0-4), Severity (0-3)	0-12	0-5
Aberrant Motor Behavior	Frequency (0-4), Severity (0-3)	0-12	0-5
Sleep	Frequency (0-4), Severity (0-3)	0-12	0-5

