8.3.6.2 Time to Emergence or Worsening of Neuropsychiatric/Behavioral Symptoms

The NPI scale will be used to evaluate the emergence or worsening of specific neuropsychiatric symptoms (NPS) of interest. Emergence of a NPS is defined as an NPI sub-item score = 0 at baseline that becomes ≥ 3 at subsequent study visit. The NPS of interest are the following:

- Cluster 1: Irritability, anxiety, depression/dysphoria
- Cluster 2: Agitation/Aggression, aberrant motor behaviours
- Cluster 3: Delusions, hallucinations

The catergories for NPS emergence or worsening are defined by NPI sub-item score (frequency × severity, Table 14):

- Baseline NPI sub-item score < 3 increases to NPI sub-item score ≥ 3 on one or more of Cluster 1 NPS
- Baseline NPI sub-item score < 3 increases to NPI sub-item score ≥ 3 on either agitation/aggression or aberrant motor behaviours of Cluster 2 NPS
- Baseline NPI sub-item score < 3 increases to NPI sub-item score ≥ 3 on either delusions or hallucinations of Cluster 3 NPS

Time-to-Event Analysis

The time-to-event is measured from day of randomization to day of earliest emergence or worsening of a NPS (NPI sub-item score) based on the above definitions. Emergence is defined as a NPS with NPI sub-item score = 0 at baseline and becomes > 0 at a subsequent study visit. Worsening is defined as a NPS with NPI sub-item score of 1 or 2 at baseline and becomes \geq 3 at a subsequent study visit. Subjects who do not experience the event by the study's end or drop out for other reasons will be censored. The same statistical analysis methods will be employed as in Section 8.3.6.1.

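### The protocol describes an NPI with no frequency rating, while the SAP scores each item as frequency × severity; one of the two is wrong as written

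*Protocol*

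**What the plan says.** Protocol 7.1.11.7 sets out the form step by step. Each of 12 domains opens with a yes/no question. If the answer is yes, "the informant then rates both the Severity of the symptoms present within the last month on a 3-point scale" and also rates caregiver distress on a 5-point scale. The section then lists the outputs: "The NPI provides symptom Severity and Distress ratings for each symptom reported", and "total Severity and Distress scores reflecting the sum of individual domain scores". Frequency is not among them. The background in Protocol 2.3.1.1 likewise describes the NPI in terms of presence and severity only.

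The SAP (8.2.4, NPI-12 paragraph and Table 14) describes a caregiver form of the same kind: "It is a self-administered questionnaire completed by caregivers about subjects for whom they care". It scores it differently. It states that "The NPI assesses the neuropsychiatric or behavioral symptoms of AD, including their frequency and severity", and that "each item has score range of 0-12 with a NPI-total score range of 0-144" for the subject's symptoms, with 0-60 for caregiver distress. Table 14 gives each item a frequency of 0-4 and a severity of 0-3, and incomplete totals are prorated to a maximum of 144.

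SAP 8.3.6.2 defines the sub-item score as the product of frequency and severity and builds its time-to-event rules on it, for example: "Baseline NPI sub-item score < 3 increases to NPI sub-item score ≥ 3 on one or more of Cluster 1 NPS". It also defines emergence twice: once as 0 at baseline rising to at least 3, and once as 0 rising to anything above 0.

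**The concern.** A product score needs both factors. A site that followed the protocol text would collect severity and distress but no frequency, and the SAP's NPI total could not then be calculated.

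Two planned analyses depend on that score. Change from baseline in NPI at Weeks 26, 52 and 78 is an additional secondary endpoint (SAP 5.2.2), analysed by MMRM (SAP 8.3.3). Time to emergence or worsening in three symptom clusters (SAP 8.3.6.2) uses the sub-item score and a cut-off of 3. If the missing factor came to light only after unblinding, the replacement score and event definition would have to be chosen with treatment assignments known.

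This does not look like a declared change. SAP Section 5 explains why DAD and the imaging and fluid biomarkers were re-designated relative to Protocol version 3.0, but says nothing about NPI scoring.

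**Working it through.** **Inputs.** From Protocol 7.1.11.7: 12 domains, 3-point severity, 5-point distress, no frequency. From SAP Table 14: 12 items, frequency 0-4, severity 0-3, distress 0-5. From SAP 8.3.6.2: sub-item score = frequency × severity, cut-off 3.

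**Assumptions.** (a) The protocol does not give codes for its 3-point scale; I take 1-3 for a present symptom and 0 for an absent one, in line with the SAP's 0-3. (b) A present symptom has frequency of at least 1 and severity of at least 1.

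**Step 1: the SAP's own ranges.** Item maximum 4 × 3 = 12; total 12 × 12 = 144; distress 12 × 5 = 60. All three reproduce, but 144 does so only if every item has a frequency rating.

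**Step 2: the protocol's ratings alone.** Item maximum 3; severity total 12 × 3 = 36. The ratio of maxima is 144 / 36 = 4.

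**Step 3: can the SAP total be recovered from severity?** With frequency between 1 and 4 for each present symptom, a severity total S is compatible with any SAP total from S (all frequencies 1) to 4S (all frequencies 4). For S = 12 that is 12 to 48. No rescaling removes this uncertainty.

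**Step 4: can the cut-off of 3 be determined?**

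| Severity | Products at frequency 1, 2, 3, 4 | At least 3? |
|---|---|---|
| 0 | 0 | never |
| 1 | 1, 2, 3, 4 | depends on frequency |
| 2 | 2, 4, 6, 8 | depends on frequency |
| 3 | 3, 6, 9, 12 | always |

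On the product score, 2 + 3 + 4 = 9 of the 12 non-zero combinations meet the cut-off. If the same cut-off were applied literally to a 0-3 severity score, only severity 3 would meet it, that is, 4 of those 12 combinations. The same written rule would define a narrower event. The baseline condition (score below 3) is undetermined for severities 1 and 2 in the same way.

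**Step 5: what survives without frequency.** Severity 0 and severity 3 are settled. The emergence rule of 0 to above 0 needs only presence, so it can be applied.

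**Step 6: proration.** With one item missing the factor is 144/132 = 36/33 = 12/11; with two missing it is 144/120 = 36/30 = 1.2. The factor is the same on either scale, so the constant does harm only if 144 is combined with item maxima of 3.

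**Step 7: distress.** The protocol's 5-point scale coded 1-5 gives a maximum of 60, matching the SAP; coded 0-4 it gives 12 × 4 = 48. The SAP range of 0-5 has six values, so the coding of an absent symptom needs to be stated.

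**The case against.** The strongest reply is that the protocol paragraph may simply be an incomplete description of a form that does record frequency. Both documents call it the 12-item NPI, both say caregivers complete it, and both cite the same 1997 source. The protocol paragraph is loosely written: it has caregivers completing the form and then has trained site staff administering it to the subject. The neighbouring QoL-AD section has a similar slip, with 13 items, then a 15-item version said to add four. The SAP was written after enrolment closed and gives rating-level ranges for every item.

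That stands as a live explanation. A reader might infer that two different instruments are in use, or that the SAP score cannot be computed. The documents do not support either conclusion, because the eCRF and the NPI form are not among them. They show a contradiction, not missing data. The reply does not remove the contradiction, however: the protocol is silent on NPI frequency throughout, and no text reconciles it with Table 14.

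A reader might also infer that every event rule in SAP 8.3.6.2 would fail, or that the cut-off is meant to pick out milder but frequent symptoms. Neither follows. The 0 to above 0 rule needs only presence, and every severity-3 combination meets the cut-off, even at frequency 1.

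**Conclusion.** The inconsistency is real and one document needs correcting. Whether data are affected depends on a single fact outside the documents: whether a frequency rating was collected.

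If it was, the SAP scoring works and only the protocol text is wrong. If it was not, then on the assumed 0-3 severity coding the score runs to 36 rather than 144, the SAP total is known only to within a factor of 4, and the cut-off of 3 is undetermined for severities 1 and 2.

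The weight is moderate. NPI is outside the graphical testing procedure, and SAP 8.1.5 treats p-values for such endpoints as nominal. ADAS-Cog 13, A-IADL and CDR-SB do not use the NPI, so nothing here bears on the trial's main conclusion. The double definition of emergence needs settling whichever form was used: a move from 0 to 1 or 2 is an event under one wording and not under the other.

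**What to change.** Before unblinding:

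1. Check the eCRF and the NPI form for a frequency field.
2. If it is present, correct Protocol 7.1.11.7 to describe the frequency rating and the product score. The SAP scoring stands.
3. If it is absent, restate SAP Table 14, the item range (0-3), the total range (0-36), the proration maximum (36) and the cut-offs in 8.3.6.2 on the severity score. The new cut-offs should be chosen deliberately: carrying 3 over unchanged would restrict events to the top grade.
4. In either case, keep one emergence definition in 8.3.6.2 and make the cluster rules agree with it.
5. In either case, state the distress coding so that the protocol's 5-point scale and the SAP's 0-5 range match.

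The cost is one check of the form and wording changes, mostly in a single document. If frequency is absent, the derivation programs for the NPI total and the time-to-event variables also change. No new data collection is proposed.
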